11.1.3. AK Lesion Eligibility

To be eligible for this trial, the Treatment Field must contain **4-8 AK lesions** that meet each of the following criteria:

- a. Grade 1 or 2 AK lesions only - not Grade 3; The definitions of AK Grades to be used for eligibility purposes are as follows:
 - Grade 1 – mild (slightly palpable AK that are felt better than seen)
 - Grade 2 – moderate (moderately thick AK that are easily seen and felt)
 - Grade 3 - severe (very thick, obvious, and/or hyperkeratotic AK). Treatment Fields selected for this trial must **not** contain any Grade 3 AK lesions.
- b. located on the subject's head including the face or balding scalp but not on the lips, ears, submandibular area, or neck;
- c. located in an area of the subject's head that easily visible to the subject in a mirror;
- d. discrete (i.e., no borders that are clearly touching one another);
- e. a maximum diameter 10 mm (inclusive) in any direction; and

- f. not atrophic, pigmented, or Bowenoid.

AK lesions grades will not be recorded in the CRF since the AK lesion grades are not an endpoint in this study.

11.2. Treatment Field Selection

Any 25 cm² contiguous area on the face or scalp of the subject that contains 4-8 AK lesions that meet the requirements stated in AK Lesion Eligibility criteria (Section 11.1.3) may be selected as the study Treatment Field. The Treatment Field will be selected at Screening and confirmed on Day 1 Pre-Dose. If the Treatment Field selected at Screening is no longer eligible at Day 1 Pre-Dose, a new Treatment Field must be selected on Day 1 Pre-Dose.

The Treatment Field must be a single, contiguous 25 cm² area that is easily visible to the subject when looking in the mirror. The Treatment Field should include at least 4 but not more than 8 AK lesions all of which must be Grade 1 or 2 AK lesions. The ideal Treatment Field should optimally be square or rectangular and not irregular, to simplify study drug application by the subject.

The Treatment Field or its outer border must not be:

- a) An area of skin that received any AK or other medical or physical treatment within 4 months of the Day 1 Visit (Exclusion Criterion #14);
- b) Within 2.5 cm (~1 inch) of either labial commissure of the mouth, lip vermilion border, palpebral fissure or a suspected malignancy;
- c) Close to another active dermatologic process that could spread to the Treatment Field and interfere with the proper assessment of the Treatment Field and/or its included AK lesions;
- d) So close to the eyebrows, beard, or other area with hair as to interfere with proper application of the study drug or assessment of the Treatment Field.

NOTE: Ideally other AKs should NOT be adjacent to the border of the Treatment Field which could confound the AK lesion counting or identification of the Treatment Field at subsequent study visits.

11.3. Study Tools

The following four (4) study tools will be used for Treatment Field selection, AK Lesion counts, Study Drug measurement, and Study Drug Application. The preliminary tools will be supplied by the Sponsor. Investigators (or designee) will prepare the final tools for use by the sites and the subject based upon the instructions provided by the Sponsor.

1. **Treatment Field Map** - This flexible, 8.5 x 11-inch plastic transparency with 1 cm x 1 cm grid printed on the surface will be used by the Investigator (or designee) to: (a) define a Treatment Field at Screening and Day 1 Pre-Dose Visits; (b) count AK lesions in the Treatment Field; and (c) to create the Treatment Field Template. Instructions regarding use of this tool will be distributed to the site.

2. **Treatment Field Template** – The tool consists of a clear, thin, flexible, 8.5 x 11-inch plastic transparency sheet supplied by the Sponsor marked by the Investigator (or designee) with landmarks (e.g. eyebrows, ear helix, and/or nevi) to guide the subject to the proper placement of the sheet. The template also includes a cut-out hole that will act as a stencil, guiding the Subject (or dosing partner) to the precise Treatment Field for application of the study drug. This template (stencil) will be used by the:
- Investigator (or designee) (a) to train the subject in proper identification of their unique Treatment Field; and (b) to train the subject in precise study drug application to their unique Treatment Field.
 - Subject (or dosing partner): (a) to identify their unique Treatment Field and (b) to apply the study drug precisely to their Treatment Field.

Instructions regarding use of this tool will be distributed to the site.

3. **Dosing Card** – a, thin plastic card with a rectangle printed on the middle of the card. A strip of ointment expressed from the study drug tube that fits the clear portion of the rectangle is the correct approximate dose of study drug to be applied to the Treatment Field. A new previously unused Dosing Card will be used for each application by the subject to measure their proper study drug dose and will be discarded after use.

Instructions regarding use of this tool will be distributed to the site.

4. **Treatment Field Photograph** – At least 1 standard facial photograph that includes the Treatment Field and its surrounding landmarks may be taken of each subject. The sole purpose of this photography to supplement the use of the Treatment Field Template in guiding the site and the subject to the subject's precise Treatment Field. The photograph that best represents the Treatment Field will be printed. The site personnel will label the photograph with "left" and "right" as well as point out landmarks on the picture to subject (e.g. moles, eyebrows, or nose) in order to properly orient the subject. The subject will be given the labelled photograph for use with the template and retention in the subject's source documentation.

12. CONDUCT OF THE STUDY

12.1. Study Blinding and Randomization

12.1.1. Study Blinding

This is an open-label study. Therefore, no one will be blinded.

12.1.2. Randomization

Subjects who pass screening and are eligible for enrollment will be consecutively enrolled into Part A (Cohort 1) and Part B (Cohort 2). There will be no need for randomization in Part A or Part B.

Subjects enrolled into Part C will be randomly assigned to Cohort 1 or to Cohort 2 at a ratio of 1:1 to allow for equal expansion of the number of subjects into each of these cohorts. Details regarding the randomization technique(s) will be detailed in the SAP. On Day 1 Pre-Dose, after confirming the subject's eligibility, the Investigator (or his designee) will approve the subject's unblinded randomization. Subjects will be randomized in a fashion that will maintain a balance between the 2 cohorts across all subjects enrolled (not per site) and notify the site of the result.

12.2. Pre-Screening

Sites are encouraged to pre-screen subjects prior to consenting. The FDA guidance regarding which pre-screening procedures may be performed may be found on the FDA web site at: <http://www.fda.gov/RegulatoryInformation/Guidances/ucm126430.htm>.

12.3. Subject Informed Consent

No activities other than pre-screening procedures (including Screening activities) may be performed before a fully executed IRB approved current informed consent form (ICF) has been obtained, with a copy of the ICF given to the subject and another copy placed in the subject's medical records.

Information about the study, explaining the objectives, procedures, and potential risks versus benefits will be given to the subject in writing and verbally in a language that is understood by the subject. The subject should have adequate time to read the information and to ask the Investigator any questions. The Investigator must be satisfied that the subject has understood the information provided in the ICF before written consent is obtained.

12.4. General Considerations

12.4.1. Demographics

The birth date, gender, race, and ethnicity of each subject will be documented.

12.5. Study Periods

This study will consist of the following periods:

- Screening Period: Days -21 through Day 1 Pre-dose
- Treatment Period: From Day 1 Dosing through Week 12 Visit (Day 1 Dosing - Day 85)
- Post-Treatment Follow-Up Period: Between Week 13 and Week 16 Visits (Day 85 – Day 113)

12.6. Study Procedures per Period and Visit

12.6.1. Screening Period

The Screening Period begins immediately following the ICF signing (see Section 12.3 for a description of the informed consent procedures).

✓ *Screening Visit (Day -21 to Day -1)*

The following procedures are to be performed during the Screening Visit:

- Site personnel confirm that the ICF: (a) is the most current ICF; (b) was signed and dated both by the subject and investigator or designee; and (d) was copied with one copy given to the subject for their personal records. The process of the informed consent should be documented in the subject's medical records.
- Demographics recorded
- Medical (and surgical) history recorded
- Prior concomitant medications
- Adverse events that occur following ICF signing will be recorded.
- Height and weight recorded.
- Vital Signs: oral temperature, peripheral blood pressure, heart rate, and respiratory rate will be recorded
- Clinical laboratory tests including hematology, chemistry, coagulations, and urinalysis: Fasting status will be recorded.
- Urine beta-HCG will be performed on all women
- 12-lead ECG tracing recorded. An original duplicate copy of the recorded ECG is required for trial documentation. This ECG will also be transmitted electronically to the central ECG laboratory.
- Scalp and face examination by PI (or designee) with selection of a Treatment Field that is anticipated to meet the criteria stated in Section 11.2 at the Day 1 Visit
- AK lesion count (Section 11.1.1)
- Supervised study drug measurement and application training (see Section 13.6.3). The Treatment Field Map and Template will be prepared as per the Investigator. Subject will

be trained to measure (using placebo ointment on the Dosing Card) and to accurately apply the study drug, without actually applying placebo ointment to their Treatment Field.

- Subject instructions will be reviewed including appointment for the next visit
- Inclusion and exclusion (enrollment) criteria applied by Investigator and recorded

✓ ***Day 1 Pre-Dose Visit***

Subjects who have completed all screening procedures and continue to meet the study enrollment criteria will return to the investigative site on Day 1 Pre-Dose. During this visit, the following procedures will be performed:

- Vital signs: oral temperature, peripheral blood pressure, heart rate, and respiratory rate will be recorded
- Adverse event(s): volunteered, elicited, and observed AEs will be recorded
- Concomitant medications documented
- Treatment Field selection/confirmation
- The Treatment Field photograph, Map, and Template will be prepared.
- Supervised study drug measurement and application training (see Section 13.6.3). Subject will be trained to measure (using placebo ointment on the Dosing Card) and to accurately apply the study drug, without actually applying placebo ointment to their Treatment Field.
- Physical examination (Section 10.3.3)
- Local Skin Reaction Score of the skin around the AK lesions in the Treatment Field (baseline)
- AK Lesions in the Treatment Field: baseline count (Section 11.1.1)
- Clinical Laboratory tests including hematology, chemistry, and urinalysis. Fasting status should be recorded.
- Urine beta-HCG test will be performed on all women and results recorded.
- 12-lead ECG tracing will be recorded. An original (duplicate) copy of the ECG is required for trial documentation. This ECG will also be transmitted to the central ECG laboratory
- Repeat supervised study drug measurement and application training (see Section 13.6.3) will occur a 2nd time at the end of the Day 1 Pre-Dose Visit. Subject will be tested as to whether they can measure (using placebo ointment on the Dosing Card) and to accurately apply the study drug, without actually applying placebo ointment to their Treatment Field. Subjects (or their dosing partners) who fail to measure and/or apply the study drug properly will be screen failed.
- Enrollment criteria and safety data (from Screening and all available data from the Day 1 Pre-Dose Visit) will be reviewed and approved by the Investigator (or designee)

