10.3.7. Local Skin Reaction Score

The Investigator (or designee) will use the Local Skin Reaction (LSR) Score (see Section 22.1) to numerically assess the overall degree of erythema, edema, weeping / exudate, vesicles, erosions / ulcerations, scaling / dryness, scabbing / crusting as well as the Subjective LSR Score (Section 0) to assess itching and pain in the Treatment Field. The assessments will use a 5-point scale, from 0 (none/trace) to 4 (extreme). This assessment will be performed on Day 1 Visit and repeated at each subsequent visit. The individual scores for each potential finding will be recorded in the respective cells by the assessor.

Whenever possible, the same investigator should perform all of these assessments.

In this trial LSRs will be collected independent of AEs. Details regarding LSR reporting are included in Section 15.1.

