12.6.2. Treatment Period

✓ *Day 1 Dosing Visit*

The following procedures will be performed on subjects selected to proceed to the Treatment Period.

- Study drug accountability and dosing compliance: Study drug tube will be designated and a Dosing Diary will be provided to the subjects.
- Used and new study drug tubes will be weighed and the results recorded.
- Study drug application and completion of the Dosing Diary by the subject under the supervision of the site personnel.
- Subject instructions will be reviewed including appointment for the next visit. Study drug and study tools will be given to the subject.

✓ *Day 1 Post-Dose through Week 4 Visit*

- Subjects will dose at home and record each application in the Dosing Diary.
- Study drug application:
 - Subjects in Cohort 1 will apply study drug twice daily. On Day 1 subjects in Cohort 1 will apply the second dose at home in the evening.
 - Subjects in Cohort 2 will apply study drug once daily.
- Site personnel will communicate with the subjects approximately 2 weeks after Day 1 (Section 12.7) to review the trial instructions and Dosing Diary as well as to remind each subject of their next site visit. Subjects will be reminded to bring all study drug with them to the next visit.

✓ *Week 4 Visit*

On Day 29 (± 5 days) the following procedures will be performed:

- Adverse event(s) AEs will be recorded
- Concomitant medications documented
- Vital signs: peripheral blood pressure, respiratory and heart rates, and oral temperature will be recorded
- Physical examination
- Local Skin Reaction Score in the Treatment Field
- AK Lesions in the Treatment Field: count (Section 11.1.1)
- Study drug accountability and dosing compliance: Used study drug tube will be collected and new tubes designated. Dosing Diaries will be collected and reviewed with the subject, and a new diary will be provided to the subjects.
- Used and new study drug tubes will be weighed and the results recorded.

- Study drug application and completion of the Dosing Diary by the subject under the supervision of the site personnel.
- Trial instruction review including an appointment for the next visit will be given. Study drug and study tools (as required) will be re-supplied to the subject, as needed. Subjects will be reminded to bring all study drug with them to the next visit.

✓ ***Week 5 through Week 8 Visit***

- Subjects will dose at home and record each application in the Dosing Diary.
- Study drug application:

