17.4. Safety Assessments

The safety endpoint data will be summarized for the ITT population. AEs will be categorized by System Organ Class (SOC) and Preferred Terms (PT) using the Medical Dictionary for Regulatory Activities (MedDRA version 19.1 or higher). The incidence of AEs, as well as the intensity and relationship to study drug will be summarized by cohort. Safety will also be assessed by evaluating findings of physical examinations, vital signs, clinical laboratory test results, 12-lead ECG tracings, Local Skin Reaction Score, drug exposure, concomitant medications, Urine Pregnancy Test results, withdrawals/terminations, and dose adjustments. These findings will be summarized and compared to findings from baseline evaluations.

Local Skin Reaction (LSR) Scores will be summarized.

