22. APPENDICES

22.1. Local Skin Reaction Score

The Local Skin Reaction Score is an assessment of the skin in the Treatment Field. At each study visit the Investigator (or designee) will assign a severity score to each of the objective findings listed in the table. **Whenever possible, the same investigator should perform all the LSR assessments.**

The Investigator will assess the selected Treatment Field and rate the findings on a 5-point scale (0-4). The composite LSR score will consist of the sum of all the individual LSR scores.

Local Skin Reaction	0 NONE	1 MILD	2 MODERATE	3 SEVERE	4 EXTREME
Erythema	None or Pinkish-red over isolated portions of the Treatment Field	Pinkish-red over most of the Treatment Field	Red	Intense redness (beet red)	Very intense redness that extends >2 cm beyond the Treatment Field
Edema / Swelling	None or Trace edema	Slightly palpable or barely visible edema	Visible and easily palpable edema	Gross edema	Gross edema that extends >2 cm beyond the Treatment Field
Weeping / Exudate / Crust	None	Mild weeping or exudate	Moderate weeping, exudate or crust	Thick exudate or crust over >50% of the Treatment Field	Heavy exudate or crust that extends >2 cm beyond the Treatment Field
Vesicles / Pustules	None	Vesicles with limited coalescing	Vesicles over >50% of the Treatment Field with majority coalescing	Pustulation	Coalesced pustules
Flaking / Scaling	None or Trace flaking/scale	Mild flaking or light scale	Moderate flaking and/or scaling over >50% of Treatment Field	Severe, thick scale	Severe, thick scale that extends >2 cm beyond the Treatment Field
Erosion / Ulceration	None	Scattered shallow erosions	Deep erosions over >50% of the Treatment Field or limited areas of ulcerations	Small eschar or extensive ulcerations	Eschar that covers the entire Treatment Field

The 5-point LSR Score is: **0 = No or Trace Reaction, 1=Mild Reaction, 2=Moderate Reaction, 3=Severe Reaction, and 4=Extreme Reaction.**

In this trial Local Skin Reactions (LSRs) will not be recorded as AEs unless they (a) require treatment with a prescribed medication; (b) extend >2 centimeters beyond the border of the Treatment Field; or (c) require a study drug dose adjustment.

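### Section 12.6.1 limits the baseline Local Skin Reaction score to skin around the lesions, while Section 10.3.7, Appendix 22.1 and every later visit score the Treatment Field

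*Combined protocol and SAP*

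**What the plan says.** **Area scored at baseline.** The Day 1 Pre-Dose list in Section 12.6.1 specifies "Local Skin Reaction Score of the skin around the AK lesions in the Treatment Field (baseline".

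**Area scored later.** The Week 4, 8 and 12 procedures (12.6.2), the Week 13 and 16 procedures (12.6.3) and the Early Termination Visit (12.6.4) all read "Local Skin Reaction Score in the Treatment Field", with no limit to the skin around the lesions.

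**General definition.** Appendix 22.1 states: "The Local Skin Reaction Score is an assessment of the skin in the Treatment Field", and applies this to each study visit. Section 10.3.7 points to 22.1 and says of the score: "This assessment will be performed on Day 1 Visit and repeated at each subsequent visit".

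**Use.** Section 17.4 includes the Local Skin Reaction (LSR) score among the safety findings, then says: "These findings will be summarized and compared to findings from baseline evaluations". The synopsis identifies baseline as Day 1 Pre-Dose.

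**Items.** Section 10.3.7 lists "erythema, edema, weeping / exudate, vesicles, erosions / ulcerations, scaling / dryness, scabbing / crusting" as the objective signs. The table in 22.1 has six rows. Crust is merged into one of them ("Weeping / Exudate / Crust"), pustules join vesicles, and flaking/scaling stands where 10.3.7 has scaling/dryness. For the total, 22.1 says: "The composite LSR score will consist of the sum of all the individual LSR scores". Section 22.2 scores itching and pain on the same 0 to 4 scale as a Subjective LSR Score and does not say whether they enter that sum.

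**The concern.** A change from baseline is interpretable only if the same skin is scored both times. Section 5.2 describes actinic keratoses as lesions that are themselves red and scaly, and erythema and scaling are both LSR items. A baseline that leaves the lesions out, followed by visits that include them, can register pre-existing disease as a new skin reaction.

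Systemic and local skin tolerability is one of the primary objectives (Section 6). There is no control arm, so no concurrent untreated group would show the same rise and expose it. Under Section 15.1.2, an LSR is recorded as an adverse event only if it needs a prescribed medication, spreads more than 2 cm beyond the field, or requires a dose adjustment. Milder reactions are therefore seen mainly through this score. Section 5.6.4 says that the results will feed into Phase 3 design and dose selection.

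**Working it through.** The protocol gives no figure for this point, so there is none to reproduce. The check compares the texts and then applies the anchors in 22.1.

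**1. Which area does each text give?**

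| Source | Day 1 | Later visits |
|---|---|---|
| 12.6.1 | skin around the lesions | – |
| 12.6.2 to 12.6.4 | – | Treatment Field |
| 10.3.7 | same assessment as later visits | Treatment Field, using 22.1 |
| 22.1 | Treatment Field | Treatment Field |

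Day 1 has two incompatible instructions. Later visits have one.

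**2. How much of the field can entry lesions cover?** Inputs: 4 to 8 lesions in 25 cm² (9.1) and a maximum diameter of 10 mm (11.1.3). Lesions are assumed round.

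Covered share = n × π × (d/2)² / 25 cm²

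- 4 lesions at 10 mm: 4 × π × 0.5² = 3.14 cm², or 12.6%
- 8 lesions at 10 mm: 8 × π × 0.5² = 6.28 cm², or 25.1%
- At an assumed 5 mm diameter: 0.79 cm² (3.1%) for 4 lesions and 1.57 cm² (6.3%) for 8

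Even at the upper limit, lesions occupy about a quarter of the field.

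**3. Which anchors can lesions alone reach?**

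- Erythema 1 needs pinkish-red over most of the field. At 25.1% or less, entry lesions cannot reach it, and isolated pinkish-red is explicitly grade 0.
- Erythema 2 is simply *Red*, with no area threshold, so a red lesion could be scored 2.
- Flaking/scaling 1 is mild flaking or light scale, with no area threshold, so lesional scale could be scored 1. Trace scale is 0.
- Flaking/scaling 2 needs more than half of the field and is out of reach.
- Flaking/scaling 3, severe thick scale, has no area threshold, but very thick or hyperkeratotic (Grade 3) lesions are excluded at entry.

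**4. Assumed cases.** Surrounding skin is clear, there is no drug reaction, and lesions are unchanged at follow-up.

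| Lesional sign | Baseline, lesions out | Follow-up, lesions in | Apparent change | Change if lesions are in at both |
|---|---|---|---|---|
| isolated pinkish-red | 0 | 0 | 0 | 0 |
| light scale | 0 | 1 | +1 | 0 |
| judged *Red* | 0 | 2 | +2 | 0 |
| light scale and *Red* | 0 | 1 + 2 = 3 | +3 | 0 |

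If the lesions have cleared by follow-up, the mixed-area change is 0 in every row. With lesions in at both visits, the change is then 0, −1, −2 and −3 respectively.

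**5. Composite range, a separate matter.**

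- Objective items: 7 × 4 = 28 from 10.3.7; 6 × 4 = 24 from 22.1.
- With itching and pain added (2 × 4 = 8): 36 and 32.

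**The case against.** The strongest reply is that 12.6.1 is a stray phrase. Section 10.3.7 and Appendix 22.1 both cover Day 1 and both point to the Treatment Field, so a site working from the scoring form would use one area throughout. Sites might also leave lesions out at every visit, since the score is meant to rate skin reaction. This stands in part. A reader might infer from 12.6.1 that baseline will certainly be perilesional and every change biased upward. The documents do not support that, because they give two instructions. But the visit list is what a coordinator follows on the day, and mixed practice between sites would also make baselines non-comparable.

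A reader might suppose that lesions alone would rate erythema 1 plus scaling 1. The erythema part is ruled out by 22.1, as step 3 shows.

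A reader might blame the two item lists for the same bias. They do not cause it: the mismatch is the same at every visit and adds no lesional signal to the change. Section 10.3.7 also refers assessors to 22.1, so the six-row table is probably the working form.

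A reader might treat LSR as the main tolerability measure. Section 8 lists it beside adverse events, laboratory tests, vital signs, examinations, ECG and exposure, without ranking. Section 17.4 names no composite change score, test or threshold.

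Finally, both cohorts share the same wording, so nothing in it favours one regimen. That stands, though the artefact could differ between cohorts if clearance or site practice differs.

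**Conclusion.** The point holds as an internal contradiction with a conditional consequence. Section 12.6.1 conflicts with 10.3.7, 22.1 and all later visit procedures on the area to be scored. If sites follow 12.6.1 at Day 1 and score lesions afterwards, the change from baseline can include lesional signs that have nothing to do with the drug, and this uncontrolled design has no comparison that would show it.

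The actual size is unknown: the documents give neither the share of sites that would follow each wording nor how often lesions would be judged scaly or *Red*. The per-subject examples of 0, +1, +2 or +3 points rest on assumed lesional signs, clear surrounding skin and unchanged lesions. The artefact diminishes as lesions clear. The contradiction is worth correcting because the edit is small and an unscored baseline sign cannot be reliably recovered later. The item-list discrepancy is real but separate: it affects which signs are recorded and the composite range.

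**What to change.** **Assessment area.** Use one area at every visit, including Day 1. The simplest edit is to change the Day 1 Pre-Dose line in 12.6.1 to "Local Skin Reaction Score in the Treatment Field" followed by (baseline), which matches 22.1 and all later visits. Leaving lesions out at every visit would also be consistent, but it means rewriting 22.1 and all the later visit procedures.

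**Items.** Replace the list in 10.3.7 with the six rows of 22.1, state that the objective composite runs from 0 to 24, and say whether itching and pain are added to it or reported separately.

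**Cost.** Two short wording edits and a check that the LSR page of the CRF agrees. The edit has a statistical downside. With lesions scored at baseline, their redness and scale can fall as the keratoses clear, so a negative change may partly reflect efficacy and could offset a true drug reaction. The LSR change should therefore be read alongside lesion clearance. The edit belongs before Day 1 visits begin. If some have already taken place, the area used at baseline should be documented for those subjects.
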